2.4.6 QST protocol

A QST battery will be applied for more comprehensive sensory characterization of these patients. The QST will follow a standard protocol,³² and include the assessment of mechanical detection threshold (MDT) with Semmes-Weinstein monofilaments, mechanical pain thresholds (MPT) with standardized weighted metal probes, cold and warm detection thresholds (CDT and WDT), as well as cold and heat pain threshold (CPT and HPT) with TSA-II, and vibration detection threshold (with standard tuning fork). QST tests will be performed in the area of maximum pain and a control, non-painful area.

Thermal detection and thermal pain thresholds

Equipment: The Thermal Sensory Analyzer (TSA-II platform - Medoc, Ramat Yishai, Israel) will be used to determine thermal detection and pain thresholds. This equipment is used globally for functional assessment of pain and temperature-conducting nerve fibers (C and A-delta fibers).

Method and Background: Using the thermal sensory analyzer, cold and warm detection thresholds (CDT and WDT, respectively), as well as cold and heat pain thresholds (CPT and HPT, respectively) will be determined.^{33,34} The thermode with contact area of 9.0 cm² is applied to the tested site, and all thresholds are determined by continuous ramping of temperature from 32°C baseline temperature by 1°C/s until the subject presses the 'stop' button. Cut-off temperatures are 0°C and 50°C, to minimize thermal damage to the skin. The baseline temperature to which the thermode returns before each test is 32°C. The average threshold is calculated from three measurements in each area.

Determination of mechanical detection threshold (MDT)

Equipment: A set of standardised Semmes-Weinstein monofilaments (0.25, 0.5, 1, 2, 4, 8, 16, 32, 64, 128 and 256mN). The contact area of the filaments with the skin is of uniform size (<1 mm²) and texture.

Methods and Background: Standardised Semmes-Weinstein monofilaments will be used in a modified "method of limits" manner using 3 series of increasing and decreasing stimulus intensities to determine the geometric average as the tactile detection threshold of the affected and unaffected skin areas³⁵.

Monofilaments of different stimulus intensities are used to determine the tactile detection thresholds. A filament eliciting 16mN force* is applied first, followed by filaments of consecutively lower intensity until the patient cannot detect the stimulus being applied. This respective force represents the first threshold value. The order in which the stimuli are applied is then reversed and stimuli of consecutively greater intensity are applied until sensation is detected (this intensity becomes the second value). Again filaments with decreasing intensity are applied until in total 3 upper and lower values of detection are fulfilled from which the mechanical detection threshold can be determined.

* In case the first filament with an intensity of 16mN is not detected, the next highest intensity filament which can be detected must be used as a starting intensity. However, the relevant force of this stimulus is not documented. Filaments with consecutively lower intensity are applied until the patient cannot detect the stimulus being applied. The procedure is followed as above; until in total 3 upper and lower values of detection are fulfilled from which the mechanical detection threshold can be determined.

Determination of mechanical pain thresholds (MPT)

Equipment: A set of standardized weighted metal probes (Nervetest, MRC systems) exerting pressure of 8, 16, 32, 64, 128, 256 and 512 mN.

Methods and Background:

The standardized metal probes will be used in a modified method of levels manner, 3 series of increasing stimulus intensities to detect the mechanical pain threshold. Beginning with an applied force of 8mN, stimuli increase in intensity until the sensation induced by increased pressure can be described as "sharp". The corresponding force is used to represent the first MPT value. The stimuli are applied in the descending order, until the sensation induced by pressure is described as "blunt". The procedure is then repeated a total of 3 times and until a total of 6 values are obtained, from which the mean MPT is determined.

Determination of vibration detection thresholds (VDT)

Equipment: A standard tuning fork.

Methods and Background:

The tuning fork will be applied at the lateral malleolus, and vibration detection threshold (the moment patient stops feeling the vibration of the tuning fork applied to the skin) will be measured on a scale of 1-8. The test will be repeated a total 3 times. VDT is determined as an average of the three measures.

Determination of wind-up ratio (WUR)

Equipment: A standardized weighted metal probe (Nervetest, MRC systems) exerting pressure of 256 mN.

Methods and Background:

Wind-up ratio (WUR) to punctate mechanical stimulation (i.e. temporal summation) will be measured as another surrogate of descending facilitation. WUR will be assessed by a published protocol.^{32,36} In this test a 256mN pinprick probe (Nervetest, MRC systems, Germany) is first applied singularly and then as a series of 10 identical stimuli with 1Hz frequency within an area of 1 cm². Immediately following the single and 10 stimuli, participants rate their pain on a 0-10 NRS, and a ratio is calculated using these values. This procedure is repeated twice; a geometric 'wind-up' average is calculated from the two ratios.

Determination of conditioned pain modulation (CPM)

Equipment: A thermostat-controlled digital water bath; The Thermal Sensory Analyzer (TSA-II platform - Medoc, Ramat Yishai, Israel)

Methods and Background:

Conditioned pain modulation (CPM) is a surrogate measure of descending inhibition vs. facilitation. CPM efficiency is derived from a patient report of pain intensity following application of a calibrated painful stimulus (called test stimulus) with and without another ongoing unpleasant stimulus (called conditioning stimulus). The intensity of the conditioning and pain stimulus will be determined individually by cold temperature that elicits pain intensity of 30-70 on 0-100 NRS (conditioning), and hot temperature that elicits pain intensity of 60 on 0-100 NRS (test).

The conditioning stimulus will be applied by immersing the non-dominant or non-affected arm in a cold thermostat-controlled water bath. The initial temperature will be set to +8°C. If that temperature elicits pain intensity between 30-70 on 0-100 NRS, the CPM protocol will use +8°C conditioning. Alternatively, water temperature will be adjusted in 2°C increments (lowest will be 2°C) to elicit pain in that range.

The previously determined Pain-60 test stimulus will be applied at the dominant or affected forearm, using a 3x3 cm Peltier thermode connected to TSA-sensory analyzer (Medoc Inc, Ramat Yishai, Israel).

The length of the conditioning is 60 seconds; during the last 30 seconds, the test stimulus is applied. The difference between test stimulus intensity with and without conditioning is defined as CPM magnitude. CPM>0 (i.e. increased pain to test stimulus following conditioning) implies descending pain facilitation.^{37,38}

2.4.7 Statistical Methods

All demographic, sensory, analytical and patient-reported data will be captured on case report forms, manually entered to a Research Electronic Data Capture (REDCap) database that will be created for the project, and will be verified by an independent study team member. Plasma and CSF concentrations of ondansetron will be analyzed using a previously validated liquid chromatography method.³⁹ Non-compartmental PK analysis will be performed to construct the concentration-time curves of ondansetron in human plasma with and without tariquidar.³¹ Ondansetron concentration in CSF will be used to evaluate biodistribution of ondansetron to CNS, by the means of CSF to plasma concentration ratio. We do not expect missing outcomes data as all primary and most secondary outcomes will be collected with the participants physically present with the research team. Any missing data will be described, but no data imputation will be attempted. Intergroup comparisons for parametric data will be performed by paired t-test, and for non-parametric data by Wilcoxon signed-rank test for paired samples. McNemar's test will be used to compare paired nominal data, and Fisher's exact test to compare non-paired nominal data.

Sample size:

Change in spontaneous pain reduction (secondary outcome) was used to determine the sample size for the study. The baseline pain intensity (\pm SD) of patients with peripheral neuropathy we have recruited to various studies over the past two years have been 6.3 ± 2.1 . This proof of concept study expects to demonstrate a 30% difference in pain reduction between the two intervention sessions. Given that in a published study of IV ondansetron in NeuP a 20% pain reduction has been observed (although not different from placebo), we assume pain intensity of 5.1 ± 2.1 in ondansetron+placebo group, and expect pain intensity of 4.0 ± 2.1 in ondansetron+tariquidar group at the 60-120 minute timeframe. To determine a significant difference with two-tailed $\alpha < 0.05$ and 85% power (effect size 0.52), 28 subjects will be required in this cross-over study. We expect to enroll 28-32 participants to the study to reach 28 evaluable participants.

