2.3.1 Subject Selection

Patients with neuropathic pain meeting inclusion criteria will be recruited from the Saint Louis community until 28 participants have completed both study sessions.

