On each of the intervention dates, women of childbearing potential will undergo urine β -hCG testing, and will be excluded if pregnancy test is positive. Participants will complete a brief pain assessment, as well as WUR and CPM testing at baseline (Figure 2B). Thereafter, two IV catheters will be inserted in participants' arms. One will be utilized for drug infusion and the catheter in the contralateral arm will be used for serial blood sampling. One 5-ml blood sample will be obtained for P-glycoprotein polymorphism analysis. At study visit 1 and study visit 2, an additional 5-ml baseline blood sample will be obtained for future research with participant consent. Participants will report baseline spontaneous pain (0-10 NRS) and complete a baseline NPSI. Placebo (D5W solution) or tariquidar (4mg/kg dose) will be administered IV over 60 minutes. Starting 30 minutes after the initiation of tariquidar/placebo, a 15-min ondansetron co-infusion will be given, infused via Y-site, to time its peak brain concentration with Pgp inhibition. The intensity of spontaneous pain (on 0-10 NRS) will be assessed every 10 minutes for 60 minutes, and every 15 minutes thereafter for a total of 120 minutes, then every 30 min for a total of 240 minutes. WUR and CPM testing will be repeated 90 minutes after the end of ondansetron infusion (i.e., 105 minutes after the beginning of ondansetron infusion). Participants will record self-reported pain hourly on the study day until bedtime, and daily for 3 weeks thereafter. NPSI pain descriptors will be assessed prior to, and 70 minutes after, the beginning of ondansetron infusion. Additionally, blood samples for ondansetron concentrations will be obtained at baseline (time zero) and approximately at 15, 30, 60, 90, 120, 180, and 240 minutes from the beginning of ondansetron

infusion (See Table 1 for full summary of the measurement schedule.) Plasma will be processed and stored in aliquots at -80°C until analysis. A 3-mL CSF sample (per participant's consent) will be obtained via lumbar puncture between 30 and 180 minutes from the beginning of ondansetron infusion, for the assessment of ondansetron concentration in the CSF using population PK approach as we previously described³¹. Lumbar puncture will not be performed if participant is currently taking anticoagulant treatment or if the participant has a contraindication to the lumbar puncture per investigator discretion.

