3.3 Premature withdrawal from a study for a single patient

If at any time the constraints of this protocol are considered to be detrimental to the patient's health and/or the patient no longer wishes to continue protocol therapy, the participant will be withdrawn from the study and the reason(s) for withdrawal documented in the case report forms.

Any participant will be withdrawn from the study in the following scenarios:

- Death
- Anaphylaxis
- Allergic reaction with urticarial, rash or dyspnea,
- Cardiac arrest
- Atrial or ventricular fibrillation
- Ventricular Tachycardia
- Syncope
- AV block (2nd degree type II or 3rd degree)
- New QTc prolongation >60ms greater than baseline or >470ms for men or >480ms for women
- Troponin elevation > 0.03 ng/mL
- Sustained increase or decrease in SBP of >30 mmHg systolic or >20 mmHg diastolic
- Sustained vital sign abnormalities
 - HR<40 or >120 beats per minute
 - SpO₂ <92%
 - Temperature <36 C or >38°C
- ALT/AST \geq 3xULN AND total bilirubin \geq 2xULN
- AST/ALT \geq 8xULN
- Thrombocytopenia
- Clinically meaningful CBC abnormalities (compared to baseline)
- Altered mental status (delirium, inability to follow simple commands)
- Seizures
- Persistent visual disturbances
- General or specific changes in the patient's condition that render the patient unable to receive further treatment in the judgment of the investigator
- Suspected or confirmed pregnancy
- Serious non-compliance with the study protocol
- Lost to follow-up
- Patient withdraws consent
- Investigator removes the patient from study
- Investigator decides to close the study

If a participant withdraws from the study, the participant will be replaced in order to provide the required number of evaluable subjects. Subjects will be withdrawn if the investigator decides that discontinuation is in the best interest of the subject, or the subject requests withdrawal from the study.

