3.5.2 Potential risks from lumbar puncture

Lumbar Puncture (LP) is widely used technique of CSF sample aspiration by thin needle from the subarachnoid space of the lumbar dural sac. LP is a major diagnostic tool used in neurological clinics as relatively safe method to obtain CSF sample for further analysis. The important complication of LP is post-lumbar puncture headache (PLPH) developing within a week after LP. In a multisite international trial, 9% of 3868 enrolled patients reported PLPH,⁴⁰ with 0.3% patients requiring an epidural blood patch (procedure of introducing autologous blood into epidural space). Other adverse events were non-specific headache (10.2%), back pain (17%), nausea and/or vomiting (2.5%), dizziness (4.5%) (1.3%). Other possible complications may include bleeding as well as temporary or permanent neurological damage, although these are extremely rare. Management of these potential adverse events are described below in section 3.4.

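### The lumbar puncture behind the primary CSF:plasma ratio is by consent, so the stated reason for expecting no missing primary data fails for CSF, and no analysis that uses single samples is named as decisive

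*Combined protocol and SAP*

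**What the plan says.** The synopsis makes a higher CSF:plasma ratio with tariquidar the first hypothesis. Section 2.4.5.1 lists that ratio, compared between arms, under primary outcome measures.

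- **Sampling (2.4.3).** "A 3-mL CSF sample (per participant's consent) will be obtained via lumbar puncture", at any time from 30 to 180 minutes after the ondansetron infusion starts. The puncture is skipped for current anticoagulant treatment or for a contraindication judged by the investigator. Neither refusal nor omission is on the withdrawal list in 3.3.
- **Target and replacement.** Recruitment continues "until 28 participants have completed both study sessions" (2.3.1). When someone withdraws, "the participant will be replaced in order to provide the required number of evaluable subjects" (3.3). Neither rule mentions CSF, and the word evaluable is not formally defined.
- **Missing data and tests (2.4.7).** "We do not expect missing outcomes data as all primary and most secondary outcomes will be collected" while participants are with the research team. Missing values are to be described and not imputed. Paired comparisons use the paired t-test or the Wilcoxon signed-rank test.
- **Population PK.** The synopsis, 2.4.3, 2.4.5.1 and 2.4.5.2 assign CSF concentrations to a population PK approach. No tariquidar effect parameter, interval or test is stated for it.
- **Puncture complications.** Section 3.5.2 says: "The important complication of LP is post-lumbar puncture headache (PLPH) developing within a week after LP", and cites a 9% rate. Section 3.6.2 removes participants with severe symptoms and treats mild ones conservatively.
- **Bleeding risk (3.6.4).** Candidates are asked about clotting disorders, bleeding, liver disease and anticoagulants, and abnormal findings lead to exclusion.

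**The concern.** A participant can be in the room for both sessions and still give no CSF, or CSF from one session only. That participant counts towards the 28 and is not replaced. Presence on site is therefore no reason to expect complete data for this primary outcome.

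The only comparison tests named need a value from each session of the same participant, so a single CSF sample is lost to them. The population PK model could use it, but the plan does not say whether that model or the paired test settles the CSF question. The trial could reach its target with clearly fewer than 28 CSF pairs, no rule would flag this, and the choice of analysis would be left until the data are in.

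**Working it through.** **The plan's own figure.** The target comes from pain: "Change in spontaneous pain reduction (secondary outcome) was used to determine the sample size for the study". The statement is "85% power (effect size 0.52), 28 subjects will be required in this cross-over study", two-tailed at 0.05. The paired normal formula gives n = ((1.960 + 1.036)/0.52)² = 33.2, so 34; the exact paired t calculation gives 36. At n = 28 the power is about 79% (normal) or 76% (t). A one-sided paired t-test gives 28 with 85.0% power. If 0.524 (1.1/2.1) is instead standardised by the between-participant SD, an unstated within-participant correlation of 0.6 gives 29. This mismatch is a separate matter. What counts here is that 28 was set for pain and so secures no number of CSF pairs.

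**Inputs.** N = 28 completers (2.3.1). Uptake p per session is not given in the documents; 0.9, 0.8 and 0.7 are assumptions. The text does not say whether consent to the puncture is asked once or at each session, so both extremes are shown.

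**Formulas.**
- Independent by session: pairs = 28p²; participants with one sample = 28 × 2p(1 − p).
- Both or neither: pairs = 28p; no single samples.
- Interval width relative to 28 pairs = √(28/pairs), that is 1/p or 1/√p. This ignores the slightly larger t multiplier with fewer pairs.

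| Assumed p | Pairs, independent | Single samples | Interval wider by | Pairs, both or neither | Interval wider by |
|---|---|---|---|---|---|
| 0.9 | 28 × 0.81 = 22.7 | 28 × 0.18 = 5.0 | 11% | 25.2 | 5% |
| 0.8 | 28 × 0.64 = 17.9 | 28 × 0.32 = 9.0 | 25% | 22.4 | 12% |
| 0.7 | 28 × 0.49 = 13.7 | 28 × 0.42 = 11.8 | 43% | 19.6 | 20% |

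**Detectable effect.** This is the standardised paired effect detectable with 85% power (two-sided t, pairs rounded down). It is 0.587 at 28 pairs. Under independence it is 0.670 / 0.774 / 0.906 at 22 / 17 / 13 pairs. Under both-or-neither it is 0.625 / 0.670 / 0.727 at 25 / 22 / 19 pairs. Power for the CSF ratio itself cannot be computed, because no human within-participant SD for it is given.

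**Headache as a source of session-2 refusal.** 9% of 28 is about 2.5 participants. Severe cases are removed (3.6.2), and withdrawn participants are replaced (3.3). That leaves only milder cases who attend session 2 and decline the second puncture.

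**The case against.** The strongest counter-argument is the population PK analysis. It is planned, it appears within the primary outcome section, and it can use unpaired samples taken at varying times. A reader might infer that participants with one puncture contribute nothing to the primary question; the documents do not support that. What stands is narrower: 2.4.7 evaluates CNS distribution through the CSF:plasma ratio and names only paired tests for comparisons, and the PK model is given no treatment-effect parameter and no deciding role.

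A reader might also infer that headache after the first puncture makes CSF loss unequal enough between sessions to bias the comparison. The figures do not show that. The 9% rate bounds the headache-related loss at about 2.5 of 28, severe cases leave and are replaced, and treatment order is randomised, so session-2 losses are not tied to one arm by design.

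Two further points are fair. Section 2.4.7 says missing data are not expected, not that there will be none, and it promises to describe any. Section 3.6.4 already screens for bleeding risk, but it conflicts with 2.4.3, which keeps anticoagulated participants in the study and skips the puncture. Even if 3.6.4 governs, refusal and other contraindications remain.

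Finally, the effect may be large enough for fewer pairs: in healthy volunteers at 8 mg, CSF AUC was 28.0 against 14.1 ng·h/mL, a ratio of 1.99. Without a within-participant SD, that reassurance cannot be tested.

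**Conclusion.** The point holds for the CSF part of the primary outcome. The reason given for expecting no missing primary data is contradicted by the protocol's own consent and omission rules. Plasma PK and most tolerability measures do not depend on the puncture.

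Under the assumed uptakes, 28 completers yield roughly 14 to 23 CSF pairs with 5 to 12 single samples if decisions are independent by session, or 20 to 25 pairs and no single samples if they are both-or-neither. The interval is then 5% to 43% wider than with 28 pairs. The size rests on assumed uptake, on reading the 2.4.3 procedures as applying to each intervention day, and on taking evaluable to mean having completed both sessions.

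A reader might infer that the trial misses a required number of CSF pairs. It does not, because the documents set no such number. The defect is a wrong rationale and an undefined decisive analysis, both worth correcting before data are seen.

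**What to change.** 1. In 2.4.7, replace the rationale with a statement that CSF may be missing because the puncture is by consent and can be omitted.
2. Name one decisive CSF comparison that uses every CSF sample, paired or single. Either give the planned population PK model a tariquidar effect on CSF distribution, reported with its confidence interval, or fit a mixed model of the log CSF:plasma ratio with treatment, period, sampling time (30 to 180 minutes) and a participant random effect. Keep the complete-pair test as a sensitivity analysis.
3. Count participants with CSF and plasma from both sessions separately from session completers. State the CSF conclusion with the actual numbers of pairs and single samples.
4. Reconcile 2.4.3 and 3.6.4 on participants taking anticoagulants.

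The cost is protocol wording, a little more analysis work and a CSF number that may be below 28. No patients or procedures are added. The change recovers what single samples can offer, which is modest if a participant's two values are strongly correlated. It does not restore lost pairs: an expected 28 pairs would need 35 / 44 / 58 completers at p = 0.9 / 0.8 / 0.7 under independence (28/p²), or 32 / 35 / 40 under both-or-neither (28/p), against a planned enrolment of 28 to 32.

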2.4 Design and Procedures

2.4.1 Study Design

Randomization and Blinding: The study is designed as a prospective, randomized, double-blind, cross-over experiment in patients with neuropathic pain. After signing informed consent and meeting eligibility criteria, participants will receive two 16 mg IV infusions of ondansetron, approximately 3 weeks apart. Participants will be randomized to the order of tariquidar (4mg/kg dose in 500mL D5W) and placebo (D5W solution) co-administration with ondansetron.

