2.4.5.2 Secondary Outcome Measures

Secondary outcome measures include:

1. Change in spontaneous pain intensity (measured on 0-10 NRS) from baseline to 60-120 minutes after ondansetron IV infusion, compared between two sessions with and without tariquidar. The pain severity values obtained at 60, 90, and 120 minutes will be averaged to derive the secondary outcome measure. The values will be compared via paired t-test (or Wilcoxon signed-rank test, if data not normally distributed).
2. Changes in NPSI total score and sub-scores (burning pain, paroxysmal pain, paresthesia/dysesthesia score) will be compared between treatment sessions;
3. The association between baseline Conditioned Pain Modulation (CPM) magnitude (Δ CPM) and the % pain reduction from baseline will be determined by bivariate regression. A significant association between the two measures will be indicative of differential analgesic response as a function of descending pain modulation;

Exploratory analyses will be performed to determine if variables such as sex, weight, baseline wind-up ratio (WUR), peak ondansetron plasma concentration, and P-glycoprotein genotype affect the difference in pain reduction between the two study sessions.

A population PK approach will be used to model CSF concentrations of ondansetron with and without tariquidar co-administration.

Table 1. Study Day Timeline

	Drug	Blood*		PK		NRS	NPSI	CPM	WUR	QST	Questionnaires
Screening	TQD	OND	X	Blood	CSF	X	X	X	X	X	X
Study day (min after ondansetron infusion start)											
Baseline			X	X		X	X	X	X	X	
-30 min	TQD / placebo Infusion										
0 min		OND infusion		X		X					
10 min						X					
15 min				X							
20 min						X					
30 min				X	X**	X					
40 min						X					
50 min						X					
60 min				X		X					
70 min							X				
75 min						X					
90 min				X		X					
105 min						X		X	X		
120 min				X		X					
135 min						X					

150 min						X					
165 min						X					
180 min				X		X					
240 min				X		X					
Hourly after discharge- study day						X					
Post-study day (weeks)											
1						daily					
2						daily					
3			X			daily					

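### The crossover randomises session order, but the paired session contrasts have no period term, so a session 1 to session 2 shift in response costs precision and, if the orders are unequal, biases the estimate

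*Combined protocol and SAP*

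**What the plan says.** Section 2.4.1 sets up a two-session crossover: "Participants will be randomized to the order of tariquidar (4mg/kg dose in 500mL D5W) and placebo (D5W solution) co-administration with ondansetron". The general rule in 2.4.7 is that "Intergroup comparisons for parametric data will be performed by paired t-test, and for non-parametric data by Wilcoxon signed-rank test for paired samples". For the pain outcome, which also drives the sample size, 2.4.5.2 repeats this: "The values will be compared via paired t-test (or Wilcoxon signed-rank test, if data not normally distributed". The NPSI contrasts between sessions have no test of their own, so the general rule applies to them. For categorical outcomes, "McNemar's test will be used to compare paired nominal data, and Fisher's exact test to compare non-paired nominal data".

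None of these tests uses session order. The exploratory analyses in 2.4.5.2 ask whether "variables such as sex, weight, baseline wind-up ratio (WUR), peak ondansetron plasma concentration, and P-glycoprotein genotype affect the difference in pain reduction", and order is not among the examples listed. The three-week washout in 2.4.3 is justified by elimination of both drugs. That deals with carryover, not with a difference between first and second exposure.

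On balance, 2.4.3 mentions a randomisation schedule, but no allocation ratio, blocking or other method is described. Section 3.3 says that after a withdrawal "the participant will be replaced in order to provide the required number of evaluable subjects", with no rule for the order to which a replacement is assigned.

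**The concern.** A paired test on tariquidar-minus-placebo differences assumes that all the differences share one mean. If the second session gives a systematically different response, the differences move one way in participants who had tariquidar second and the other way in those who had it first. The plain test treats this spread as random error, although the randomised order explains it. If the two orders are unequal among completers, the movements do not cancel and part of the shift enters the estimated tariquidar effect.

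A shift is plausible here. In 2.4.7 the plan cites a 20% pain reduction after intravenous ondansetron that did not differ from placebo. A non-specific response of that kind need not be the same at first and second exposure. The infusions and the lumbar puncture are also new in session 1 and familiar in session 2. At stake are the precision of the pain and NPSI contrasts and, for an uneven split, their accuracy.

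**Working it through.** **Inputs from 2.4.7.** Expected pain is 5.1 with placebo and 4.0 with tariquidar, each with SD 2.1; two-tailed alpha 0.05; power 85%; effect size 0.52; N = 28. The difference is 5.1 − 4.0 = 1.1, and 1.1/2.1 = 0.524.

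**Assumptions.** The SD of paired differences is 2.1. This is what the stated effect size implies, and it corresponds to a within-patient correlation of 0.5. The shift p (session 2 minus session 1 response) is 0, 0.5, 1.0 or 1.5 NRS points; the documents give no value.

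**The plan's own figure.** A paired t-test with N = 28 and effect size 0.524 has two-sided power of 76%, not 85%. A two-sided test at 85% needs 35 participants, or 36 with 0.52. The figure of 28 is reproduced with one-sided alpha 0.05. That is a separate matter, but it makes 76% the starting point here.

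**Model.** Let τ be the tariquidar effect. The tariquidar-minus-placebo difference has mean τ + p in the n1 participants who receive tariquidar second, and τ − p in the n2 who receive it first.

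**Noise at 14:14.** The mean difference is unbiased, but the SD that the test sees is √(2.1² + p² × 28/27):

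- p = 0.5: √(4.41 + 0.259) = 2.16
- p = 1.0: √(4.41 + 1.037) = 2.33
- p = 1.5: √(4.41 + 2.333) = 2.60

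The shift is fixed by order rather than being normal noise, so putting these SDs into a noncentral t slightly overstates the loss (67% and 58% for the last two). Simulation of at least 100,000 trials per setting gives:

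| Shift | Plain paired t, 14:14 | Order-adjusted, 14:14 |
|---|---|---|
| 0 | 76% | 76% |
| 0.5 | 74% | 76% |
| 1.0 | 69% | 76% |
| 1.5 | 60% | 76% |

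At p = 1.0 the true standard error is still 2.1/√28 = 0.40, while the test uses about 2.33/√28 = 0.44. The plain test is therefore conservative, with type I error of about 3%.

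**Bias with unequal orders.** The bias is p × (n1 − n2)/28. For p = 1.0:

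- 16:12: 4/28 = 0.14 points
- 17:11: 6/28 = 0.21 points, or 0.21/1.1 = 19% of the planned difference
- 18:10: 8/28 = 0.29 points

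For p = 0.5 these values halve. At 17:11 with p = 1.0, power of the plain test is about 49% or 85%, depending on the direction of the shift. At 18:10 its type I error is about 7.5%.

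**Chance of such splits.** If simple 1:1 randomisation is assumed, Binomial(28, 0.5) gives probabilities of 57% for 16:12 or worse, 35% for 17:11 or worse and 18% for 18:10 or worse.

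**Order-adjusted analysis.** The estimate is the mean of the two order-specific means. Its standard error is 2.1 × √((1/n1 + 1/n2)/4), with 26 degrees of freedom. This gives 0.397 at 14:14, 0.406 at 17:11 and 0.414 at 18:10, and power of 76%, 74% and 72–73%. The bias is zero and power does not depend on p.

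**The case against.** Several points on the other side stand and limit the concern.

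- **Drift in pain level.** A reader might infer that the entry criterion of pain of at least 4 guarantees a downward drift that contaminates the comparison. The documents do not support this. The pain outcome in 2.4.5.2 is a change from baseline, and 2.4.3 takes a baseline score on each intervention date, so drift in level between sessions is largely subtracted out. A different response at second exposure is not.
- **Novelty of testing.** A reader might also infer that the pain tests are new in session 1. Section 2.4.2 has the NPSI, CPM, WUR and QST done at screening. Only the infusions and the lumbar puncture are new.
- **Size of shift.** The plan's assumed fall on ondansetron plus placebo is 6.3 − 5.1 = 1.2 points. A 1.0-point shift is about 83% of that whole response, and 1.5 points exceeds it. At 0.5 points and equal orders the loss is only about two percentage points of power.
- **Bias.** It is conditional on the achieved split and averages to zero over fair randomisation. The plan does not describe the allocation method, so it does not establish that orders will be unequal, and the 35% figure holds only under simple randomisation. If, for example, 32 were allocated 16:16 and four were lost from one order, the split would be 16:12.
- **Scope.** The contrasts that matter here are secondary outcomes in a proof-of-concept study. The CSF modelling ("A population PK approach will be used to model CSF concentrations of ondansetron with and without tariquidar co-administration") is not a paired test and lies outside this point. Nothing in the documents suggests a period shift in plasma concentrations or CSF ratios.

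None of this restores a period term to the analysis. It reduces the likely size of the effect, not the case for a near-costless correction.

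**Conclusion.** The omission is certain: order is randomised, and none of the stated session comparisons uses it. Its effect is uncertain, because it depends on a shift that the documents do not give. With no shift and equal orders, nothing is lost.

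Under the assumptions above (SD of differences 2.1, difference 1.1, 28 completers), a shift of 0.5 points at equal orders is a minor loss, and only shifts near the whole assumed placebo-session response do substantial damage. Bias of 0.14 to 0.21 points needs both a 1.0-point shift and a 16:12 to 17:11 split.

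The documents do not support a claim that the tariquidar estimate is biased by design or that false positives are generally inflated. At equal orders the plain test errs on the conservative side. This is a worthwhile improvement, mainly of precision, for the pain, NPSI and other paired continuous contrasts.

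**What to change.** In 2.4.5.2 and 2.4.7, replace the plain paired test for the pain, NPSI and other paired continuous contrasts with the standard two-period crossover analysis. For each participant, take the session 2 minus session 1 difference in the outcome. Compare these differences between the two randomised orders by two-sample t-test, or by Wilcoxon rank-sum test if they are not normal. Half the difference between the order means, with the sign set as tariquidar minus placebo, is the treatment effect. A mixed model with treatment, period and sequence and a random participant effect is an equivalent alternative. Report the period-adjusted estimate with its confidence interval, and state the number of completers in each order. Fix the wording before unblinding so that the choice is not made after a shift is seen.

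The cost is a change of wording, one degree of freedom (power 76.2% to 76.1% at 14:14 with no shift) and a small loss of precision when the orders are unequal (about 74% at 17:11 and 72–73% at 18:10). No new data or patients are needed.
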